6.9 Prior and concomitant therapy

BAY 81-8973 will be used as the sole FVIII source. Pre-medications ***to tolerate treatment with BAY 81-8973 are not allowed. Use of topical anesthetics prior to venipuncture is permitted. (as of Amd 1). Note: PTPs will continue their previous treatment up to 48 h before the first dose of BAY 81-8973 (as of Amd 3).***

All medications and blood products required by the subject during the study will be listed in the CRF. No other experimental drugs may be taken during the subject's participation in this study.

No immunosuppressive/immunomodulatory drugs may be taken during the subject's participation in the study. If such therapy is deemed necessary for the subject's welfare, or due to pre-existing illness, the situation should be discussed with the Sponsor before enrollment. Medications which cause a bleeding diathesis (for example, Aspirin® or acetylsalicylic acid) are contraindicated in any individual with hemophilia and should be avoided, except as specifically prescribed by a treating physician. Use of non-steroidal anti-inflammatory drugs, COX-2 inhibitors, or brief courses of corticosteroids to treat pain or acute synovitis, or inhaled or topical steroid medications (as for the treatment of asthma or eczema) are allowed. (as of Amd 1)

All concurrent prescription and non-prescription medications including over-the-counter and alternative preparations (including herbal remedies, vitamins, and health food supplements) ***will be recorded in the CRF (as of Amd 1)*** at screening and throughout the treatment and follow-up periods.

7. Procedures and variables

7.1 Schedule of procedures

7.1.1 Tabulated overview

Integrated Clinical Study Protocol
No. BAY 81-8973 / 13400

01 FEB 2019

Version 7.0

Page: 33 of 262

Table 7–1a: Schedule of evaluations (Part A – PTPs; >50 ED)

Assessments and procedures	Main study					Optional extension study	
	Visit 1 Screening	Visit 2 Baseline	Visit 3 Month 1 (+/- 1 week) (as of Amd 1)	Visit 4 Month 2 (+/- 1 week) (as of Amd 1)	Final visit Month 6 (Minimum 50 ED [as of Amd 1])	Extension Visit every 6 months ^e	Extension Final Visit ^e
Inclusion (date of written informed consent)	X				X		
Inclusion / exclusion criteria	X	X					
Demographic data	X						
Height, weight	X	X	X	X	X	X	X
Medical and surgical history	X						
Previous medication (medication history)	X						
Physical examination	X				X		
Adverse events	X	X	X	X	X	X	X
Vital signs	X	X	X	X	X		
Laboratory examination ^a	X				X		
HSP-70 antibodies		X			X		
FVIII baseline level and inhibitor (one stage) (Amd 3)	X				X		
FVIII level pre infusion and inhibitor (as of Amd 1)		X	X	X	X	X	X
Recovery (20-30 min after infusion) ^c (as of Amd 1)		X	X	X	X	X ^f (Amd 6)	X (Amd 6)
Pharmacokinetics (optional)					X ^b		
Infusion of study drug							
Electronic patient diary (EPD) documentation							
Healthcare Resources Utilization Questionnaire (as of Amd 1)	X (as of Amd 1)						
Interaction between subject/parent and investigator							
Concomitant medication	X						

a. Complete Blood Count (CBC), Chemistries

b. Blood samples at the following time points: before, 20-30 min, 4 h, and 24 h post-infusion following a washout of 48 h after last dose of FVIII. Exact times need to be entered into CRF

c. Measured at least 48 h after last dose of FVIII (as of Amd 1)

d. Weekly contact during Part A, monthly during extension and 1-2 weeks after last study visit extension

e. For the regular Extension Visit every 6 months, a window of ±2 weeks is allowed. The Extension Final Visit should take place no later than 2 weeks after 100 ED is achieved or until market authorization is obtained. (as of Amd 4)

f. At the first extension visit 6 months after the start of the extension and at any time in case of inhibitor development (as of Amd 6)

Integrated Clinical Study Protocol
No. BAY 81-8973 / 13400

01 FEB 2019

Version 7.0

Page: 34 of 262

Table 7–2b: Schedule of evaluations (Part B – PUPs/MTPs)

Assessments and procedures	Main study									Optional extension study		
	Visit 1 Screening ^k	Visit 2 Baseline	Combined Screening and Baseline (PUPs only) (as of Amd 6)	Visit 3 ED ~5 (as of Amd 6)	Visit 4 ED ~10 (as of Amd 6)	Visit 5 ED ~15 (as of Amd 6)	Visit 6 ED ~20 (as of Amd 6)	Interim Visit 30-40 ED (as of Amd 1)	Final Visit or 50 ED ^f	Extension Visit every 6 months ^f	Extension Final Visit ^f	
Informed consent	X		X						X			
Inclusion / exclusion criteria	X	X	X									
Demographic data	X		X									
Height, weight	X	X	X	X	X	X	X	X	X	X	X	
Medical and surgical history	X		X									
Previous medication (medication history)	X		X									
Physical examination	X		X						X			
Adverse events	X	X	X	X	X	X	X	X	X	X	X	
Vital signs	X	X	X	X	X	X	X	X	X	X (Amd 7)	X (Amd 7)	
Laboratory examination ^a	X		X						X			
HSP-70 antibodies		X ^b	X ^b						X ^b			
FVIII baseline level and inhibitor (one stage) (Amd 3)	X ^h (Amd 6)	X ^h (Amd 7)	X									
FVIII level before infusion and inhibitor ^c (Amd 1)				X	X	X	X		X	X ^j	X	
Epitope mapping (inhibitor positive patients) (Amd 4)				←----- X ^e ----->								
Recovery (20-30 min after infusion) (Amd 1)		X	X				X		X	X ^j (Amd 6)	X (Amd 6)	
Pharmacokinetics (optional) (Amd 3)				←----- X ^d ----->								
Biomarker investigation (recommended) (Amd 4 and Amd 7)				←----- X ^g ----->								
Infusion of study drug (Amd 1)				←----- continuously in accordance with the prophylaxis regimen ----->								
Electronic patient diary (EPD) documentation				←----- continuously ----->								
Healthcare Resources Utilization				←----- monthly ----->								
Questionnaire (Amd 1)				←----- weekly ----->								
Interaction between subject/parent and investigator				←----- monthly ----->								
Concomitant medication	X			←----- continuously ----->								

For footnotes please see next page

Integrated Clinical Study Protocol
No. BAY 81-8973 / 13400

01 FEB 2019

Version 7.0

Page: 35 of 262

- a CBC, chemistries; local labs as needed to reduce blood volume (Section 14.4)
- b In subjects > 7 kg at baseline visit. See recommendations for blood draws in subjects <10 kg (Section 14.4)
- c Measured at least 48 h after last dose of FVIII
- d Blood samples at the following time points: before, 20-30 min, 4 h, and 24 h post-infusion following a washout of 48 h after last dose of FVIII. Exact times need to be entered into CRF
- e Epitope mapping to be performed in combination with confirmatory retest for inhibitory antibodies (*as of Amd 4*)
- f The Final Visit can be performed as soon as a minimum of 50 ED is achieved, but no later than 2 weeks after achieving 50 ED. For the regular Extension Visit (performed every 6 months), a window of ± 2 weeks is allowed. The Extension Final Visit should take place no later than 2 weeks after 100 ED is achieved
- g The recommended biomarker investigation (pharmacogenetics) requires a separate signed informed consent (as of Amd 7). The single blood sample for this analysis can be taken at any visit except Screening, ideally at Visit 3 or whenever the subject's body weight/condition is suitable for an additional blood draw (as of Amd 4)
- h Inhibitor to be evaluated at screening (central laboratory testing), and at baseline (central and local laboratory testing), in MTPs only (ie, unnecessary to evaluate in PUPs) (as of Amd 6, include retention sample for inhibitor assessment by ELISA for MTPs). Study drug administration should start upon availability of result from local laboratory testing. (as of Amd 6 and Amd 7)
- j At the first extension visit 6 months after the start of the extension, and at any time in case of inhibitor development (as of Amd 6)
- k In case of MTPs, the screening visit should only take place after a washout period of at least 48 hours following any previous treatment with any FVIII replacement product (as of Amd 6).

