6.8 Post-study therapy

At the end of the study, all participants who *have* completed *Part A or B (as of Amd 1)* will be offered participation in an extension study. *Participation in the extension study will allow (as of Amd 1) continuation of treatment for at least 100 ED. The extension (as of Amd 1) study requires continued documentation of infusions, bleeding events, monthly interaction with the treatment center, and visits every 6 months for inhibitor testing and recovery measurements. (as of Amds 1 and 6)*

After completion of the extension study, or if the subjects or their parents/caregivers are not willing to participate in the extension study, ***treatment with study drug will end. Subsequent (as of Amd 1)*** treatment will be mutually agreed upon by the parents/caregivers and the investigator.

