 - **Serum chemistry (sodium [Na], potassium [K], bicarbonate [CO], chloride [Cl], creatinine, alanine and aspartate aminotransferases [ALT, AST], total bilirubin. (See Section 14.4 for children <10 kg) (as of Amd 1)**
- Blood sample for inhibitor testing and determination of FVIII:C trough levels (≥ 48 h after last FVIII **treatment**). (as of Amd 1)
- HSP-70 antibodies (**in children > 7 kg**). (as of Amd 1)
- **Infusion** of study drug. (as of Amd 1)
- **Vital signs after infusion**. (as of Amd 1)
- Blood sample for the determination of recovery to be taken at 20-30 min after end of **infusion**. (as of Amd 1)
- **Optional PK: Additional blood samples at 4 h and 24 h post infusion, for Part B subjects also at 20-30 min after end of infusion (can also be performed at a later visit; obtained only once during study.)**
Note to investigators: In compliance with EMA guidance and for subject safety, no more than 1% blood volume may be obtained at any one visit, and no more than 3% may be taken in one month (see Section 14.4). If additional PK samples are taken, the total volume of blood drawn in 24 h will be too high for infants weighing less than 9 kg, who must therefore be excluded from the PK sub-study. (as of Amd 1, Amd 3)
- **Recommended (as of Amd 7) pharmacogenetics in PUPs/MTPs (Part B and extension): collect blood sample for biomarker investigation, if not taken previously – requires signed informed consent. This blood draw will be done once only, and can be performed at any visit except Screening (as of Amds 4 and 6)**
- Check of EPD **entries** of interval treatment and bleeding history.

For subjects not participating in the optional extension study:

- Return of EPD
- Return of used and unused study **vials (as of Amd 1)** for final drug accountability

- **Follow-up phone call (1-2 weeks after end of treatment)**
Call parents/caregiver via telephone and review any new AEs and changes in concomitant medication since the last study visit.

For subjects participating in the optional extension study:

- Informed consent signed by parents/legal representative must be available.
- Continuation of prophylaxis treatment
- **Begin** regular **monthly** contacts between parents and the **site** to check the EPD documentation until next clinic visit. *(as of Amd 1)*

7.1.2.9 Extension study visits – 6 months after completion of Part A or B; then every 6 months (as of Amd 1)

The following procedures and assessments will be performed:

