- Measurement of body height/*length*, weight, *and vital signs (as of Amd 1 and Amd 7)*.
- **Documentation of interval history including AEs and concomitant medication and Healthcare Resources Utilization Questionnaire (Appendix 14.3).** *(as of Amd 1)*
- Check of EPD *entries of (as of Amd 1)* interval treatment and bleeding history
- Blood sample for inhibitor testing *and determination of FVIII:C trough level (≥ 48 h after last FVIII treatment) (as of Amds 1)*.
- **Blood sample for recovery measurement to be collected only at the first extension visit at 6 months. Blood sample to be taken at 20-30 min after end of infusion (as of Amd 6).**
- **Optional PK: Additional blood samples at 20-30 min, 4 h and 24 h post infusion (can also be performed at a later visit; obtained only once during study.)**
Note to investigators: In compliance with EMA guidance and for subject safety, no more than 1% blood volume may be obtained at any one visit, and no more than 3% may be taken in one month (see Section 14.4). If additional PK samples are taken, the total volume of blood drawn in 24 h will be too high for infants weighing less than 9 kg, who must therefore be excluded from the PK sub-study. (as of Amd 1, Amd 3)
- **Recommended (as of Amd 7) pharmacogenetics in PUPs/MTPs (Part B and extension): collect blood sample for biomarker investigation, if not taken previously – requires signed informed consent. This blood draw will be done once only, and can be performed at any visit except Screening (as of Amds 4 and 6)**
- **Regular monthly contacts between parents and the site to check the EPD documentation, update information on AEs and concomitant medication, completion of Healthcare Resources Utilization Questionnaire before next clinic visit. (as of Amd 1, Amd 3)**

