7.5.3.4 Inhibitor testing

Premise for inclusion **requires confirmed diagnosis of severe hemophilia A (<1% FVIII) and documentation of a (as of Amd 1)** negative test result of inhibitor at Baseline.

Blood samples for FVIII inhibitor testing will be taken at Screening (**PTPs and MTPs only**), Baseline, **at regularly scheduled intervals throughout the study, and at the (as of Amds 1 and 6)** final visit. The premise for inclusion of **PTPs and MTPs** in this study is the availability of a negative inhibitor **result (as of Amds 1 and 6)** as measured in the blood sample at Screening **and Baseline (as of Amd 7)**. A further sample will be taken at baseline before the first **infusion (as of Amd 1)**. If the inhibitor testing result changes from negative at screening

to positive at baseline, before the first *infusion (as of Amd 1)* of study medication, the subject must be withdrawn from the trial.

In Part B, the requirement for a FVIII inhibitor testing before study entry (as of Amd 1) is not applicable for PUPs but is applicable for MTPs (as of Amd 6). The absence of inhibitors will be assessed using central laboratory testing at Screening (<0.2 BU/mL), with confirmation using local laboratory testing at Baseline (<0.6 BU/mL) (as of Amd 7). After treatment is started (as of Amd 1), PUPs/MTPs must be tested for inhibitor development every 3-5 ED until 20 ED are accumulated (as of Amd 6), and at the final visit (50 ED) (as of Amd 7). Afterwards, blood samples for inhibitor testing and determination of FVIII:C trough level (>48 h after last FVIII treatment) are to be taken:

- ***every 6 months in the extension study until finalization of the study, and at the final visit (as of Amds 1 and 6).***

The laboratory analyses will be performed at central laboratories.

Investigators will be provided with a detailed laboratory manual and a copy of the individual results. Inhibitor testing will be done according to the Nijmegen modified Bethesda inhibitor assay ***at the central laboratory (as of Amd 1)***. A positive inhibitor testing is defined with a threshold of ≥ 0.6 BU in the central laboratory. Any positive test must be confirmed by a second ***plasma (as of Amd 1)*** sample ***and a determination of recovery should be performed. (as of Amd 6)***

For any subject confirmed positive for inhibitors, epitope mapping will be performed (see Section 7.6.1 for details). (as of Amd 4)

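### Table 7-2b limits the scheduled Part B extension inhibitor test to the first extension visit, while Sections 7.1.2.9, 7.5.3.4 and 6.8 give it every 6 months

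*Protocol*

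**What the plan says.** **Table 7-2b (protocol Section 7.1.1, Part B).** The row "FVIII level before infusion and inhibitor" has X with superscript j under the 6-monthly extension visit and an unqualified X under the extension final visit. The recovery row is marked the same way. Footnote j reads "At the first extension visit 6 months after the start of the extension, and at any time in case of inhibitor development".

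**Section 7.1.2.9.** Its heading sets the frequency: "Extension study visits – 6 months after completion of Part A or B; then every 6 months". The procedures listed for these visits include the inhibitor and trough sample with no first-visit limit. Only recovery is restricted: "Blood sample for recovery measurement to be collected only at the first extension visit at 6 months".

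**Section 7.5.3.4.** After the 50 ED visit, inhibitor and trough samples are due "every 6 months in the extension study until finalization of the study, and at the final visit".

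**Section 6.8.** The extension requires "visits every 6 months for inhibitor testing and recovery measurements".

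**Table 7-1a (Part A).** The equivalent footnote (f there) is attached to recovery only. The inhibitor row has a plain X at extension visits.

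**The concern.** The table and the text give different schedules for the same safety test in the same children. Sites commonly plan visits from the schedule table. Under footnote j, a Part B child with no known inhibitor has no scheduled inhibitor test at the second or any later regular extension visit. The FVIII trough sits in the same row and goes with it.

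Part B enrolls previously untreated and minimally treated children. The protocol names inhibitor development as their well-known risk (Section 1) and classes any inhibitor as a serious adverse event (Section 7.5.1.1). A missing scheduled sample can delay detection, and an inhibitor that appears and clears between samples may never be recorded. The Part B SAP (version 2.0, Section 6.2.2) dates its low-titer inhibitor period by the days on which an inhibitor is detected and is no longer detected, and it defines further inhibitor periods for the extension. An extension analysis that uses such dates depends on when samples are taken.

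Sections 6.8 and 7.1.2.9 also disagree about recovery. That is a separate and lesser matter.

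**Working it through.** The protocol gives no figure to reproduce here. The check compares the passages and then counts visits.

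**1. Passages side by side (extension, regular visits)**

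| Place | Inhibitor test | Recovery |
|---|---|---|
| Table 7-2b, footnote j | first visit, or when an inhibitor develops | same |
| Section 7.1.2.9 | every 6 months | first visit only |
| Section 7.5.3.4 | every 6 months | not scheduled here |
| Section 6.8 | every 6 months | every 6 months |
| Table 7-1a (Part A) | every 6 months | first visit, or when an inhibitor develops |

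On inhibitor testing, Table 7-2b stands alone against three text sections and the Part A table. On recovery, Section 6.8 is the outlier. The Amendment 6 copy of Table 7-2b carries a superscript on the same cell, so the mark is unlikely to be a fault of text extraction.

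**2. How long the extension lasts**

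Inputs from the protocol: the main study ends at 50 ED and the extension runs to at least 100 ED, so about 50 further ED are needed. Part B prophylaxis is at least once weekly. Regular visits fall at about weeks 26 and 52. Adherence is not given, so the values below are assumptions, and ED from bleed treatment are ignored.

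Weeks from 50 to 100 ED = 50 / (infusions per week × adherence).

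- Twice weekly, 100%: 50 / 2 = 25.0 weeks
- Once weekly, 100%: 50 / 1 = 50.0 weeks
- Once weekly, 90%: 50 / 0.9 = 55.6 weeks
- Once weekly, 80%: 50 / 0.8 = 62.5 weeks
- Once weekly, 60%: 50 / 0.6 = 83.3 weeks

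**3. Regular tests before 100 ED, text against table**

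| Dosing | Text | Table | Lost |
|---|---|---|---|
| Two or more per week | 0 | 0 | 0 |
| Once weekly, 100% | 1 | 1 | 0 |
| Once weekly, 90% | 2 | 1 | 1 |
| Once weekly, 80% | 2 | 1 | 1 |
| Once weekly, 60% | 3 | 1 | 2 |

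The final-visit test is additional and identical under both readings.

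**4. Longest untested stretch when one test is lost**

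Under the table, the stretch runs from week 26 to the final visit, taken here at 100 ED.

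- 90% adherence: 55.6 − 26 = 29.6, about 30 weeks
- 80% adherence: 62.5 − 26 = 36.5, about 37 weeks

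Under the text, the week-52 test caps the stretch at 52 − 26 = 26 weeks. The increase is therefore 29.6 − 26 = 3.6 weeks at 90% and 36.5 − 26 = 10.5 weeks at 80%.

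**5. Longer stays**

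By extension length, regular tests under text against table are 1 v 1 at 6 months, 2 v 1 at 12, 3 v 1 at 18 and 4 v 1 at 24. If the extension ends at exactly 12 months, the second regular visit coincides with the final visit and the loss is only nominal.

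**The case against.** The strongest reply is that one superscript conflicts with three consistent text sections, so most sites would test every 6 months anyway, and that little is lost even where they do not. Section 4 plans a 6-12 month extension. Section 6.1.1 allows frequency to rise as needed, and treating bleeds adds ED. Final-visit testing is unqualified, and Section 14.5 requires testing when an inhibitor is clinically suspected. The protocol places the main risk in the first 20 ED, where testing every 3-5 ED is untouched. All of this stands and limits the size of the problem. It does not remove the contradiction. A slow accruer with no known inhibitor is not reached by footnote j's second clause, because without a test nobody knows that an inhibitor has developed.

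A reader might infer two stronger consequences, which the documents do not support.

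- **That the table removes the titers needed to judge immune tolerance induction.** A child on that treatment has already developed an inhibitor, so footnote j's second clause can apply. Sections 4 and 6.1.5 separately require inhibitor levels to be collected and documented for these children.
- **That the inhibitor rate is biased low.** The Part B SAP reports Part B without the extension (Section 4.4), and its supplement takes inhibitor incidence over the total Part B period (Section 2.1). That estimate cannot be affected. In the extension, a persistent inhibitor would still be found at the final visit. Only an unknown number of transient inhibitors could be missed.

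**Conclusion.** The contradiction is real and stands in the current protocol text. Its effect is confined to the extension: possible later detection, and possibly some missed transient inhibitors, in Part B children who have no known inhibitor and accrue ED slowly.

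The loss is zero at full weekly adherence or at two or more infusions per week. It is about one scheduled test per child for continued once-weekly dosing at 80-90% adherence, and more only in longer stays. These counts rest on assumed adherence, nominal visit times and no ED from bleeds. Bleed treatment would shorten the extension and reduce the loss, and the ±2 week visit window could move the stretches slightly.

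The point is worth correcting because it concerns a scheduled safety test in the population at highest inhibitor risk and costs almost nothing to resolve. It gives no reason to doubt the planned Part B inhibitor summary.

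**What to change.** Reconcile Table 7-2b with Sections 7.1.2.9, 7.5.3.4 and 6.8 on inhibitor testing in the extension. If Sections 7.1.2.9 and 7.5.3.4 state the intended rule, remove superscript j from the extension cell of the Part B inhibitor row, leaving a plain X as in Table 7-1a, and keep j on the recovery row. If the table states the intended rule, the three text sections must change instead.

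Separately, reconcile the recovery wording in Section 6.8 with Section 7.1.2.9.

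The cost under the first option is one superscript and one sentence in an amendment, plus a note to sites with children already in the extension. It adds no test beyond those that Sections 7.1.2.9 and 7.5.3.4 already require.

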7.1.2 Timing of assessments

The main study consists of a Screening period *followed by at least 50 ED* per subject. *The Screening and Baseline visits may be combined to one visit for PUPs. There is no minimum interval between the Screening and Baseline visits for PUPs/MTPs (as of Amd 6) or PTPs. For PTPs, no longer than 8 weeks should pass between Screening and Baseline visits. (as of Amd 1)*

In Part A, PTPs, a minimum of 50 ED will be accumulated during a 6 month treatment period. Visits are scheduled at Month 1, Month 2 and Month 6. (as of Amd 1)

In Part B, the treatment period will be extended until 50 ED have been accumulated. The duration of Part B will vary and is dependent upon the frequency of prophylactic infusion and the number of bleeding events. Blood sampling for inhibitor testing is required every 3-5 ED up to 20 ED, and again at 50 ED. As most subjects will begin prophylaxis 1x week, study visits during the first 20 ED are expected to occur monthly. However, it is understood that bleeding events resulting in added doses, delayed start of prophylaxis after first bleeds, or missed infusions due to difficult i.v. access may result in some variation in the number of ED a subject has obtained at each visit or the exact interval between visits. Likewise, those subjects who receive more frequent infusions may require study visits more often than once a month. (as of Amd 1)

After completing Part A or B, all (as of Amd 1) subjects will be offered continued treatment in an extension study until a total number of at least 100 ED per subject are accumulated. Participation will require (as of Amd 1) additional visits every 6 months.

